6. TREATMENTS

6.1. Investigational Medicinal Products Used in the Study

IMP is defined as the test IMP and matching placebo IMP to the test IMP.

Refer to [Table 6](#) for a description of the test IMP (TV-44749) and placebo IMP.

The test IMP and placebo IMP are not authorized products.

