4.3.4. Handling of Adverse Events with Missing Dates

For the purpose of this study, oral olanzapine is not considered an IMP. Any adverse event with incomplete start dates will be handled as described below, and end dates will not be imputed.

- If only the start day of an adverse event (but not the month) is missing, then the start day will be imputed as the first day (01) of the month, unless otherwise specified. If the adverse event month is not missing and it is the same month as that of randomization, the start date will be imputed as the first IMP administration date during that month.
- If both the day and month are missing and the year is the year of the date of first study treatment then the date will be imputed as the date of first IMP administration, unless the adverse event end date occurred prior to the date of first study treatment, in which case the start day-month will not be imputed. In addition, if the date of first IMP administration year is < the year of the adverse event start year then the start day-month will be imputed as 01 and January, respectively.

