8. SAFETY ANALYSIS

8.1. General

Safety analyses will follow the safety estimand approach using the safety analysis sets.

Safety will be assessed by qualified study personnel by evaluating reported adverse events (including serious adverse events, extrapyramidal symptoms, injection pain, injection site findings and Injection Site Reactions [ISRs]), vital signs (blood pressure, pulse and orthostatic changes, and temperature), body weight and BMI, laboratory tests, ECG, concomitant medication use, time to all-cause discontinuation, all-cause discontinuation rates and discontinuation rates due to adverse events (tolerability), time to all discontinuation by reason, and safety rating scales (including Abnormal Involuntary Movement Scale [AIMS], Barnes Akathisia Rating Scale [BARS], Simpson-Angus Scale [SAS], C-SSRS, and CDSS).

Safety assessments and time points are provided in Table 1 (for Period 1) and Table 2 (for Period 2) of the study protocol.

The safety analysis will be performed separately for Period 1 and for the integrated study periods.

The safety analysis for Period 1 will be performed by treatment group and overall (total).

The safety analysis for the integrated study periods that will be presented in the CSR and in the IDMC closed reviews, will be performed by treatment group. Specifically, for IDMC closed reviews, patients rolling over from Placebo group will be distinguished from patients who continued their active treatment assignment from Period 1. Data from Period 1 for placebo patients will not be included in the integrated summaries.

For the open sessions of the IDMC reviews, data from Period 1 and from Period 2 will be presented separately. Summary tables will be generated for each period and will only be presented as a single total column.

For the following safety variables: Adverse events, Clinical laboratory results, ECG, weight and BMI and Vital signs, a separate safety summary will be presented for the 'While on Treatment' period, defined as the period between the first IMP administration visit until and including the End of Treatment visit (including the Early Termination visit if conducted during this period). In addition a separate safety summary table and listing will be presented for the Follow-Up period, defined as the period after the End of Treatment/Early Termination visit until the end of the study.

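### SAP 4.3.4 dates year-only adverse events from the first IMP injection or 1 January, so former-placebo patients' events on TV-44749 can be counted as Period 1 placebo events and left out of the integrated tables

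*SAP*

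**What the plan says.** Protocol 6.1 makes IMP cover both products: "IMP is defined as the test IMP and matching placebo IMP to the test IMP". SAP 4.4 takes the first administration in Period 1 as the start of treatment. For a placebo patient, the first IMP is therefore a placebo injection.

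SAP 4.3.4 handles incomplete onset dates as follows:

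- Day and month missing, first-treatment year: "the year is the year of the date of first study treatment then the date will be imputed as the date of first IMP administration". The one safeguard is "unless the adverse event end date occurred prior to the date of first study treatment".
- Day and month missing, later year: "then the start day-month will be imputed as 01 and January, respectively".
- Day alone missing: "then the start day will be imputed as the first day (01) of the month, unless otherwise specified". If the month is known and "it is the same month as that of randomization, the start date will be imputed as the first IMP administration date during that month", that date is used instead.

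No branch refers to the first TV-44749 injection or to Visit 11.

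Three other sections decide what follows. SAP 8.4 allocates an event to a period by its start. SAP 8.1 states: "Data from Period 1 for placebo patients will not be included in the integrated summaries". SAP 8.2 counts TV-44749 exposure in former-placebo patients from Visit 11.

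**The concern.** The date rule suits a trial with one treatment start. Here about a quarter of patients have two: placebo at Visit 2 and, if they continue, TV-44749 at Visit 11. Elsewhere the SAP resets these patients for the integrated analysis: baseline (4.2), treatment group (3.3), exposure (8.2) and time to discontinuation (9.2). The imputed onset of an adverse event is not reset.

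An event that began on TV-44749 can therefore be given a date in the placebo period. It is then tabulated under placebo in Period 1 and, under SAP 8.1, is missing from the integrated drug tables, while the patient's drug exposure stays in the denominator. The safety of TV-44749 is a secondary objective, so its event counts should not depend on how an unknown date is filled in.

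**Working it through.** The plan states no figure for this rule, so there is none to reproduce. The check applies the rule to dates.

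**Year-only onsets.** Let v be the Visit 2 date. Visit 11 is nominally v + 56 days. Take an event with true onset on or after Visit 11.

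- Onset in the year of v: the imputed date is v, which precedes Visit 11. Misassigned.
- Onset in a later year: the imputed date is 1 January of that year. Misassigned if Visit 11 falls after that 1 January.

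Together, a year-only on-drug event is misassigned exactly when it falls in the calendar year of Visit 11, unless Visit 11 is itself on 1 January.

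Examples:

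- Visit 2 on 10 May 2023, Visit 11 on 5 July 2023, event on 20 September 2023 recorded as 2023: dated 10 May 2023, on placebo. Wrong.
- Visit 2 on 1 December 2023, Visit 11 on 26 January 2024, event on 15 June 2024 recorded as 2024: dated 1 January 2024, on placebo. Wrong.
- Visit 2 on 10 May 2023, event on 15 February 2024 recorded as 2024: dated 1 January 2024, after Visit 11. Period correct.

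**Share misassigned.** Assumptions: Visit 2 dates uniform over a window, injections exactly 28 days apart, onsets uniform from Visit 11 to week 56. The documents give the first screening as Q4 2022 (Protocol 4.1) or Q1 2023 (SAP 2.1) and 675 randomized by 29 January 2024, so four windows were tried.

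| Visit 2 window | Misassigned | via first IMP date | via 1 January | Misassigned, first 28 days after Visit 11 |
|---|---|---|---|---|
| 1 Oct 2022 to 29 Jan 2024 | 57.1% | 34.9% | 22.2% | 94.0% |
| 1 Jan 2023 to 29 Jan 2024 | 56.2% | 42.5% | 13.7% | 96.3% |
| 1 Mar 2023 to 29 Jan 2024 | 51.5% | 35.4% | 16.1% | 95.7% |
| 1 Jan to 31 Dec 2023 | 53.7% | 38.9% | 14.8% | 96.0% |

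Hand check: let Visit 11 be uniform over one year, with 48 × 7 = 336 days on drug. A patient with r days left in the year has a share min(r, 336)/336 misassigned. The average is (336/2 + 29)/365 = 197/365 = 54%. For the first 28 days it is (28/2 + 337)/365 = 351/365 = 96%. Both agree with the table.

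**Day-missing onsets.** The result depends on which randomization SAP 4.3.4 means.

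- Period 1 randomization only: an onset in the calendar month of Visit 11 goes to day 01. Misassigned: 4.4% of day-missing on-drug events, and 52% to 53% in the first 28 days.
- Visit 11 re-randomization included: 0.04% overall and 0.5% in the first 28 days. The remainder arises when Visit 7 and Visit 11 share a month, because the first IMP in that month is then placebo.

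**Patients exposed to the rule.** 675 × 1/4 × 440/640 = 116. This applies the planned overall completion to the placebo arm and assumes that every completer enters Period 2.

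**Share of all on-drug events in these patients.** The documents give no rate of partial dates. Assume 1% to 3% of onsets are partial, with one in ten of those year-only (55% misassigned) and the rest day-missing on the less favourable reading (4.4%). The weighted share is 0.9 × 0.044 + 0.1 × 0.55 = 0.095. The affected share is then 0.01 × 0.095 = 0.1% to 0.03 × 0.095 = 0.3%. If every partial date were year-only, the upper figure would be 0.03 × 0.55 = 1.7%.

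**The case against.** The strongest answer is that very few events will be affected. Protocol 8.1.2 requires adverse events to be asked about at every contact, and Period 2 contacts are weekly. Missing data are queried (Protocol Appendix J), serious event reports include the onset date (Protocol 8.1.6.1), and SAP 4.3 leaves listings unimputed. That stands, and it limits the size.

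Three stronger readings are tempting and are not supported.

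- A reader might infer that the error always favours the drug. It does not. In patients on TV-44749 from the start, the same rule pulls Period 2 events back into the Period 1 drug columns. All four Period 1 columns can gain events, so the distortion of the Period 1 comparison with placebo is at least partly offset. Only the integrated tables err in one direction.
- A reader might infer that any partial date is almost certain to be misassigned. About 95% holds only for year-only events in the first 28 days on drug. Over all year-only on-drug events it is about half, and for day-missing events it is 4.4% or 0.04%. SAP 9.2 uses the Period 2 randomization day for former-placebo patients in the integrated periods, and SAP 3.1 recognises an assignment at Visit 11. Both lend support to the reading that gives 0.04%, although SAP 4.3.4 does not say so.
- A reader might take the loss from the integrated tables as settled. SAP 8.1 excludes placebo patients' Period 1 data, but SAP 8.4 says that an event starting in Period 1 and ending in Period 2 is shown once in the integrated table, with no exception for placebo. A misdated event that resolves in Period 2 fits that description, so the two sections conflict.

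It can also be said that the redacted SAP 4.3.2 may hold further rules. It may, and the redaction is not held against the plan. But SAP 4.3.4 is the section on missing event dates, and its text is fully visible.

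**Conclusion.** The point holds for year-only onsets in patients who moved from placebo to TV-44749. SAP 4.3.4 gives such an event a date before the first TV-44749 injection whenever it falls in the calendar year of Visit 11. Under uniform accrual and onset that is 52% to 57% of year-only on-drug events, and 94% to 96% in the first 28 days after Visit 11. The event becomes a Period 1 placebo event and, if SAP 8.1 governs, leaves the integrated drug tables while the exposure remains. Day-missing events in the Visit 11 month are affected only if the randomization in SAP 4.3.4 means Period 1 alone, apart from the small Visit 7 remainder.

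The number of affected events is not given and is probably small: roughly 0.1% to 0.3% of on-drug events in about 116 patients, on the stated assumptions. The case for a change is that the rule gives a wrong attribution, is out of step with the rest of the SAP, and is cheap to correct.

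**What to change.** In SAP 4.3.4:

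1. For patients randomized to placebo in Period 1 who received TV-44749: when the known parts of the onset date and the end date are compatible with onset on or after the first TV-44749 injection, impute the later of the date under the existing rule and the date of that injection. A year-only onset in a year that ended before Visit 11 is not compatible and keeps its present date.
2. State that the month of randomization includes the month of the Visit 11 re-randomization.

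Then reconcile SAP 8.1 with SAP 8.4 on whether a former-placebo patient's event that starts in Period 1 and continues into Period 2 appears in the integrated table.

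The rule should not rely on the visit at which an event was first recorded, because Protocol 8.1.2 does not list that among the recorded items.

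The cost is a few sentences and a small change to the date derivation. By construction, no on-drug event with a partial date in these patients would then be dated before Visit 11. The price is that some true placebo-period events with partial dates will be counted on TV-44749, so the drug counts become slightly less favourable, which is the cautious direction for safety.

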4.3.5. Handling of Concomitant Medication with Missing Dates

For determination of prior vs. concomitant medication, missing start or end month are imputed to January or December, respectively, and missing start or end days are imputed to day 01 and 30, respectively, unless the month is not missing then a missing day is imputed to 28. Missing dates for oral Olanzapine administered in the screening period (as part of the predefined study procedures, in accordance to the description in the study protocol) will not be imputed.

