6.7. Prior and Concomitant Medication or Therapy

Any prior or concomitant medication a patient has had within 30 days before IMP administration and up to the end of study, including FU, will be recorded on the CRF. Trade name and international nonproprietary name (if available), indication, dose, and start and end dates of the administered medication will be recorded. The sponsor will encode all medication according to the World Health Organization drug dictionary.

The following medications will be prohibited during this study:

- antipsychotics other than the study treatment
- strong or moderate inhibitors of CYP1A2 within 14 days or 5 half-lives (whichever occurs last) prior to randomization
- strong inducers of CYP1A2 within 30 days prior to randomization
- dopamine reuptake inhibitors or prescription psychostimulants
- opiates or opiate-containing analgesics within 14 days prior to randomization
- In addition to those listed above, medications that may be expected to significantly interfere with the metabolism or excretion of olanzapine, may be associated with a significant drug interaction with olanzapine, or may pose a significant risk to patients' participation in the study.

- Olanzapine (except when given according to the study protocol)

Allowed medications in this study include rescue medications (Section 6.7.1.1), protocol-approved antidepressants (including selective serotonin reuptake inhibitors [other than fluvoxamine], serotonin and norepinephrine reuptake inhibitors, and trazodone), and mood stabilizers (except carbamazepine) (Section 6.7.1.2), medications required for the treatment of any adverse events, and contraceptives as per [Appendix E](#).

Medications prescribed for the treatment of chronic medical conditions, other than antipsychotic medications, or for the treatment of acute medical conditions (such as antibiotics) may be permitted per investigator judgment.

COVID-19 and seasonal flu vaccines will be allowed during the study. Other vaccinations may be allowed after consultation with the MM or sponsor.

A partial list of additional disallowed medications is provided in [Appendix G](#). In the event that a new concomitant medication not specified in this protocol is initiated by the patient, the investigator is encouraged to approach the MM or the sponsor to discuss.

It is advised not to allow benzodiazepines and anticholinergics within 8 hours or 12 hours, respectively, of rating scales' assessments.

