In addition, any use of prohibited antipsychotics after early termination is not considered an ICE. Prior antipsychotic medications without a defined end-date are not deemed as ICE of "prohibited concomitant antipsychotic medication" since these cases occur before randomization and initiation of treatment.

Table 1: Classification of Intercurrent Events

Intercurrent Event	Strategy	Handling of Intercurrent Events

 • Early discontinuation of treatment due to: 
 ◦ lack of efficacy ◦ disease progression • Prohibited antipsychotic (with the exception above) 	Hypothetical	Measurements after ICE will be removed and replaced with imputed data using reference-based (CIR) imputation (assuming MNAR)

 • Early discontinuation of treatment due to other reasons (including due to adverse event) 	Hypothetical	Measurements after ICE will be removed and replaced with imputed data based on randomized treatment group (assuming MAR)

 • Allowed concomitant medications • Adverse event that did not lead to treatment discontinuation • Use of prohibited medications that are not antipsychotic • Short term use of prohibited antipsychotic (see meeting the definition above) • Injection site reaction • Out of window safety assessments 	Treatment policy	Measurements after ICE will be included in the primary analysis

ICE=intercurrent event; MAR=missing at random; MNAR=missing not at random; CIR = copy increments in reference

Any data collected after the intercurrent event (ICE) of taking prohibited antipsychotic medications (except as described above) or withdrawal from randomized treatment due to insufficient clinical response (i.e., lack of efficacy) will be treated in the analysis as MNAR. An ICE of early discontinuation for other reasons will be treated in the analysis as if the patient fully complied and completed the study (i.e., assuming missing at random [MAR]); see Table 1 for further details on the classification and handling of ICEs. This complies with the hypothetical approach.

For ICEs that were not foreseen at the time of writing the protocol and that require the use of the hypothetical strategy, classification as MAR/MNAR and revisiting this classification will be done in a blinded manner on a case-by-case basis prior to database lock for efficacy and will be

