After approximately 440 patients complete the week 8 visit, depending on the need for additional data on exposure or safety, the placebo treatment group may be discontinued and additional patients may be randomized to the study (ie, to Period 1) to the TV-44749 active treatment groups only. For further details, see Section [2.2.2 Discontinuation of the Placebo Treatment Group](#).

During the conduct of this study, an Independent Data Monitoring Committee (IDMC) will review accumulated unblinded safety, pharmacokinetic, and efficacy data on a regular basis, as detailed in the IDMC charter, to evaluate the safety of the product for the purpose of ensuring the continuing safety of the study patients and overseeing study conduct issues, as applicable. The IDMC will not evaluate efficacy for early efficacy or early futility.

Once all patients completed Period 1, and Period 2 is ongoing, an analysis of the full efficacy data will be performed.

Screening (up to 8 days Prior to Randomization to Period 1):

Patients will undergo screening procedures and assessments up to 8 days prior to randomization to Period 1. Patients will provide informed consent at the screening visit before any study-related procedures are performed. Patients will be asked to consent to share their information with a vendor that will verify that they are not currently participating or have not recently participated in another clinical study, unless prohibited by local requirements. [REDACTED]

[REDACTED]

[REDACTED]

[REDACTED]

[REDACTED]

[REDACTED]

Patients with exacerbation that started \leq 8 weeks prior to screening (the investigator should confirm the exacerbation based on the patient's medical records and/or based on anamnesis) and who would benefit from psychiatric hospitalization or continued hospitalization for symptoms of schizophrenia may be included in this study.

The patient's total Positive and Negative Syndrome Scale (PANSS) score should be between 80 and 120, inclusive, at screening with a score \geq 4 on at least 2 of the following 4 items of the PANSS positive sub-scale: hallucinatory behavior, delusions, conceptual disorganization, or suspiciousness/persecution.

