5.5. Prior Therapy and Medication

Any prior therapy, medication, or procedure a patient has had within 30 days before IMP administration and up to the end of study, including FU, will be recorded on the CRF. The trade name and international non-proprietary name (if available), indication, dose, and start and end dates of the administered medication will be recorded. The sponsor will code all medication according to the World Health Organization drug dictionary (WHODRUG GLOBAL B3 March 1, 2023 or later version).

The incidence of prior therapies and medications will be summarized using descriptive statistics by therapeutic class and preferred term. Patients are counted only once for each therapeutic class category, and only once for each preferred term category. Prior therapies and medications will include all medications taken and therapies administered before the first day of study drug administration.

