8.10. Concomitant Medications or Therapies

Concomitant therapies and medications, including medications that are taken on an as needed basis and occasional therapies, will be monitored and recorded during the study. Details of prohibited medications may be found in Section 6.7 of the study protocol. All concomitant medications will be coded using the WHO Drug.

The incidence of concomitant therapies and medications will be summarized by therapeutic class category and preferred term using descriptive statistics. Patients are counted only once in each therapeutic class, and only once in each preferred term category. Concomitant therapies and medications will include all medications up to the end of study as defined in the study protocol. This will also include medication that a patient had started taking before entering the study as long as the patient had continued to take this medication during the study.

A separate summary will be presented for Period 1 and for the integrated study periods. A separate safety summaries will be presented for the On Treatment period (baseline visit until EOT visit, including ET if conducted during this period) and for the Follow-Up period (any visit after the End of Treatment/Early Termination visit until the end of the study).

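### SAP 4.3.5 sets a missing medication start day to the 28th when the month is known, so a drug begun before the first dose in that same month is usually dated on or after it

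*SAP*

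**What the plan says.** SAP Section 4.3.5 states its purpose and the month rule together: "For determination of prior vs. concomitant medication, missing start or end month are imputed to January or December, respectively". For days, "missing start or end days are imputed to day 01 and 30, respectively", followed by the exception "unless the month is not missing then a missing day is imputed to 28". The exception speaks of a missing day in general. The section has no cap at a recorded end date and no comparison with the date of first dose. Its only exemption is for oral olanzapine given as a study procedure at screening.

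The two classes that the rule feeds are defined elsewhere in the SAP:

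- **Prior (Section 5.5):** "Prior therapies and medications will include all medications taken and therapies administered before the first day of study drug administration".
- **Concomitant (Section 8.10):** a drug begun before study entry counts "as long as the patient had continued to take this medication during the study".

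Protocol Section 6.7 sets what is recorded: "Any prior or concomitant medication a patient has had within 30 days before IMP administration and up to the end of study". SAP Section 2.1 sets the length of screening: "Patients will undergo screening procedures and assessments up to 8 days prior to randomization to Period 1".

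For comparison, SAP Section 4.3.4 handles adverse events with a known start month and a missing start day. It uses day 01, or the first IMP date if the month is that of randomization.

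**The concern.** When the month is known, day 28 is close to the latest date a start could have. Day 01 then survives for a start only if the month is missing as well, which is the reverse of what the default suggests was wanted.

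Two errors follow from applying the sentence literally. A drug begun before the first injection in that calendar month is dated on or after the injection. A drug with a recorded end earlier in that month gets a start later than its end.

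At stake is the split that the rule exists to make. A drug taken before dosing can be left out of the prior-medication summary. If it also stopped before dosing, it has not continued into the study, so it can be missing from the concomitant summary too.

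**Working it through.** The plan gives no figure to reproduce. The check applies the written rule to a calendar.

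**Inputs**

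- Imputed start: day 28 of the recorded month (SAP 4.3.5, literal reading).
- First-dose dates: all 365 days of 2023 (assumption).
- True starts: each of the 8 days before dosing (screening length, SAP 2.1), or each of the 30 days before dosing (recording window, Protocol 6.7).
- Every combination has equal weight (assumption). The results are shares of date combinations, not patient counts.

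**One example (assumed dates).** First dose 15 March; start recorded as March, day missing; recorded end 10 March. The imputed start is 28 March, which is 28 − 15 = 13 days after the first dose and 28 − 10 = 18 days after the drug stopped. Judged by its start, it is not prior. Judged by its end, it is not concomitant.

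**Step 1. Start moved to or past the first dose.** A combination counts as moved when day 28 of the start month is on or after the dose date. If the true start was in an earlier month, day 28 of that month always precedes the dose, so nothing moves. In the same month it moves whenever the dose is on or before the 28th.

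| Window | Moved / all combinations | Moved / same-month combinations |
|---|---|---|
| 8 days | 2,256 / 2,920 = 77.3% | 2,256 / 2,488 = 90.7% |
| 30 days | 4,536 / 10,950 = 41.4% | 4,536 / 5,373 = 84.4% |

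Hand check in one 30-day month: pairs with start before dose number 30 × 29 / 2 = 435. Those with the dose on or before day 28 number 28 × 27 / 2 = 378. The share is 378 / 435 = 86.9%, inside the 84.4% to 90.7% range.

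**Step 2. Start placed after the recorded end.** Take all day pairs within one month with true start on or before the end. The imputed start exceeds the end when the end day is 27 or earlier.

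- 2023 calendar: 4,536 / 5,738 = 79.1%.
- One 30-day month: pairs 30 × 31 / 2 = 465; end by day 27 gives 27 × 28 / 2 = 378; 378 / 465 = 81.3%.

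The simpler ratio 27 / 30 = 90% would be too high, because it ignores that a drug cannot end before it starts.

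**Step 3. The same check with start day 01.** Moved combinations are 0 of 2,920 and 0 of 10,950. Day 01 also cannot fall after a recorded end in the same month. This tests only drugs that truly began before dosing; the opposite error is taken up under the objection and the fix.

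**The case against.** **The exception may have been meant for end days only.** Day 28 exists in every month and day 30 does not, so this intention is plausible. But the sentence does not limit itself to end days, and a programmer following it would apply it to starts.

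**Many records may classify correctly anyway.** A drug with a recorded end before the first dose was taken before dosing, which satisfies Section 5.5 whatever start is imputed. This stands if the programming looks at the end date. The SAP does not say which date decides, so loss from the prior table is possible rather than certain.

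**Day 01 has the opposite error.** A drug truly begun after the first dose in that month would be dated before it and may be listed as prior. This stands, as a small cost. Section 4.3.4 is not a full precedent either, since in the randomization month it uses the first IMP date.

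**A stronger reading is tempting.** A reader might infer that an antipsychotic tapered at screening, with its start moved to the 28th, would be flagged as prohibited use on treatment, and its later PANSS values replaced by reference-based imputation. The documents do not support this. Section 4.3.5 limits the rule to the prior/concomitant split. The exemption in Section 1.2.1, "Prior antipsychotic medications without a defined end-date are not deemed as ICE", turns on a missing end date, not an imputed start day. SAP Appendix B takes the antipsychotic event from use documented in the CRF and reviewed blinded at the statistical data review meeting. Nothing makes an imputed start date trigger an intercurrent event.

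**Conclusion.** The concern holds as a defect in a stated rule. Read literally, Section 4.3.5 dates about 84% to 91% of same-month, pre-dose starts with a missing day on or after the first dose. Where start and recorded end share a month, it puts the start after the end in about 79% to 81% of day pairs.

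The scope is narrow. It needs a missing start day with a known month. For the first error, the start must also fall in the calendar month of the first dose, with that dose on or before the 28th. It would be wrong to read the rule as moving pre-dose medications in general: over the full 30-day window the share is 41.4%, and drugs begun in earlier months are not moved past the dose.

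The consequence is confined to the descriptive prior and concomitant medication tables. The documents do not give the number of partial dates, which is probably small. No effect on intercurrent-event classification or on the primary analysis is claimed. The percentages rest on equal weighting of calendar dates and on the literal reading of the exception.

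**What to change.** Replace the exception in SAP Section 4.3.5 with separate rules for a known month: a missing start day becomes 01, a missing end day becomes the last day of that month, and an imputed start is never later than a recorded end date. Using the last day rather than 28 also avoids ending a drug before a first dose given on the 29th to 31st when it may have continued.

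Add that imputed dates are not used to decide antipsychotic intercurrent events, which stay with the blinded review of CRF data. This contains the one downside, that a drug truly begun after the first dose in that month may also appear as prior.

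The cost is one or two sentences and a small programming change. Trial conduct, sample size and the efficacy analyses are untouched.
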